#### **Recording Adverse Events**

Adverse events spontaneously reported by the subject and/or in response to an open question from the study personnel or revealed by observation will be recorded during the study at the investigational site. Information about AEs will be collected from the Test Article Dispensation until the end of the study. Serious Adverse Event information will be collected from Test Article Dispensation until 7 days following Visit 4 (Post-use Visit). The AE term should be reported in standard medical terminology when possible. For each AE, the investigator will evaluate and report the onset (date and time), resolution (date and time), intensity, frequency, relationship to test article, action taken, serious outcome (if applicable), and whether or not it caused the subject to discontinue the study.

Intensity will be assessed according to the following scale:

- Mild (awareness of sign or symptom, but easily tolerated)
- Moderate (discomfort sufficient to cause interference with normal activities)
- Severe (incapacitating, with inability to perform normal activities)

It is important to distinguish between serious and severe AEs. An AE of severe intensity may not be considered serious.

Relationship to test article will be assessed according to the following scale:

- Not Related - A clearly evident relationship to other etiologies exists and/or the event is not temporally consistent with test article use.
- Unlikely - Based upon available information, a causal relationship to test article is improbable. Usually, another cause is most plausible.
- Possible - Event follows a reasonable temporal association with test article use and is clinically/biological plausible. Other etiologies are also possible.
- Probable - A reasonable temporal sequence of the event with test article use exists and based upon the medical professional's clinical experience, the association of the event with test article seems very likely.

- Definite - Event is clearly related to article use. It is temporally associated with test article use, follows a known or expected response pattern, and improves when stopping test. Other causes do not appear to explain the event.

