3.1. Overall Design

This study is an open-label, randomized, crossover study designed to validate that changes to the design of [REDACTED] tampons meet defined user needs. Subjects will be assigned to either a regular absorbency arm or super absorbency arm. Subjects will test a new tampon design (test tampon) and a commercially available tampon design (reference tampon).

Each tampon type will be used over the course of one menstrual cycle. Within each absorbency arm, subjects will be randomized to the order in which to use the test tampon and the reference tampon. Subject participation in the study will last over the course of 2 menstrual cycles, or approximately 2 months.

A subset of 120 subjects (60 subjects within each absorbency arm) will undergo gynecological examinations prior to and following tampon use. For the subset of subjects undergoing gynecological exams, the study will include a total of 4 visits, 2 visits for each menstrual cycle. The first visit will be the screening visit and the first pre-use visit. The next visit will be the first post-use visit, followed by the second pre-use visit and the second post-use visit. Pre-use visits will be conducted within 72 hours prior to expected menstruation and post-use visits will be conducted within 72 hours following the last tampon use for that menstrual cycle. Gynecological examinations will be performed at each visit. This subset of subjects will also complete a packaging and labeling interview at the first visit to assess whether subjects can identify and distinguish key information on the product packaging.

For the remainder of subjects who will not undergo gynecological examinations, the study will include 3 visits: a screening/pre-use visit and 2 post-use visits. Post-use visits will be conducted within 72 hours following the last tampon use for that menstrual cycle.

All subjects will keep a diary during menstruation with entries for each tampon used and will collect each used tampon to be returned to the site. At each post-use visit, site personnel will review subject diaries for completeness and accuracy, record the number of used and unused tampons returned, and evaluate used tampons to assess tampon integrity. Subjects will be considered to have completed the study after they complete the second post-use visit. Refer to the Schedule of Events (Table 1) for more details.

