6.1.5. Data Adjustments/Handling/Conventions

All collected data will be presented in listings. Data not subject to analysis according to this plan will not appear in any tables or graphs but will be included only in the data listings.

Adverse events will be coded using the Medical Dictionary for Regulatory Activities (MedDRA; version 25.1) thesaurus. Concomitant medications will be coded using the World Health Organization Drug Dictionary (WHO-DD) Enhanced B3 (September 2022).

The first article insertion date will be the date of the first tampon insertion, that the subject reported, but only for a tampon that has both the date of the tampon's insertion and the date of the tampon's removal documented in the diary. The last article's removal date will be defined in the same manner. The first insertion and last removal dates within each menstrual cycle will be identified using a similar logic but using the data from each menstrual cycle.

In case the subject didn't report the tampon's insertion and removal dates for the 1st menstrual period in the diary but returned at least 1 used tampon from 1st menstrual cycle and has available diary data for the 2nd menstrual cycle, then the first article insertion date and last article removal date for the 1st menstrual cycle will be calculated from the date of post-use visit 2 with the

assumption, that number of days between first tampon's insertion and post-use visits are the same for both menstrual cycles.

If partial adverse event onset dates or partial medication dates occur, the convention for replacing missing dates for the purpose of statistical analysis is as follows: if just day is missing then the day assigned is the first day of the month or the date of first test article insertion (if in the same month), whichever is later; if just month is missing then the month assigned is the month of the first test article insertion, unless that results in a date before the first test article insertion in which case the month after the first test article insertion is used; and if both month and day are missing then the month assigned is the month of the first test article insertion and the day assigned is either the first day of the month or the first test article insertion date, whichever is later.

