If partial adverse event onset times occur, the convention is as follows: if the missing time occurs on the day of the first test article insertion and both the hour and minute are missing then the time assigned is the time of the first test article insertion, otherwise if both the hour and minute are missing and the date is not the date of first test article insertion the time assigned is 12:00; if the date is the same as the date of the first test article insertion and only hour is missing the hour assigned is 12 or the hour of first test article insertion, whichever is later, and if the date is the same as the date of first test article insertion and only the minute is missing the minute assigned is 30 or the minute of first test article insertion, whichever is later. Otherwise the hour assigned is 12 if the hour is missing and the date is not the same as the date of first test article insertion and the minute assigned is 30 if the the date is not the same as the date of first test article insertion.

The following precaution will be considered when applying these conventions to adverse event onset dates and times: if the missing date and time reflect the date and time of onset of an adverse event, the modified date and time will be constructed to match the first documented date/time post test article administration while preserving the order in which the adverse event (AE) was reported in the CRF.

7. Study Subjects and Demographics

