9.1. Adverse Events

All AEs and serious adverse events (SAEs) will be coded using the MedDRA v. 25.1.

All AE data will be summarized for 3 periods: before any test article use, during and following test tampon use, during and following reference tampon use. AEs will be assigned to an analysis period based on the below criteria. The criteria for assigning AEs to an analysis period will differ depending on the type of test article (reference or test tampon) first used by the subject.

Test article order	Criteria for assigning AEs to analysis periods
Reference tampon → Test tampon	If the start date of the adverse event was before the date of first insertion of a reference tampon, then the AE will be assigned to the “before any test article use” period. If the start date of the adverse event was on or after the date of first insertion of a reference tampon, but before the date of first insertion of a test tampon, then the adverse event will be assigned to the “during and following reference tampon use” period. If the start date of the adverse event was on or after the date of first insertion of a test tampon, then the adverse event will be assigned to the “during and following test tampon use” period.

Test tampon → Reference tampon	
If the start date of the adverse event was before the date of first insertion of a test tampon, then the AE will be assigned to the “before any test article use” period.
 
If the start date of the adverse event was on or after the date of first insertion of a test tampon, but before the date of first insertion of a reference tampon, then the adverse event will be assigned to the “during and following test tampon use” period.
 
If the start date of the adverse event was on or after the date of first insertion of a reference tampon, then the adverse event will be assigned to the “during and following reference tampon use” period.

--------------------------------	--

An overall summary of AEs will be provided; this will present number and percentage of subjects who reported at least 1 of the following: any AE, AEs by maximum severity, AEs by maximum relationship to study product, AEs by maximum frequency, and SAEs.

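### Partial adverse event onset dates are filled in without the second product's first insertion date, so most second-product events lacking the day count under the first product; the AE tables' percentage base also disagrees with their own N.

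*SAP*

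**What the plan says.** **Period assignment.** SAP 9.1 sorts AEs into three periods using each product's own first insertion. In the reference-then-test order, for example, an AE belongs to the test tampon "If the start date of the adverse event was on or after the date of first insertion of a test tampon".

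**Partial dates.** SAP 6.1.5 gives three rules for onset dates:
- Day missing: "if just day is missing then the day assigned is the first day of the month or the date of first test article insertion" (the insertion date applies only if it is in the same month), whichever is later.
- Month missing: the month of first insertion, or the next month if the result would precede first insertion.
- Month and day missing: "if both month and day are missing then the month assigned is the month of the first test article insertion", with the day set to the later of the 1st and the first insertion date.

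First insertion here means the first documented tampon of the study, whichever product it was. The same section derives cycle-level dates ("The first insertion and last removal dates within each menstrual cycle will be identified using a similar logic") but does not use them in these rules.

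**Precaution.** SAP 6.1.5 adds that a missing AE onset is to be "constructed to match the first documented date/time post test article administration". It also asks that AEs stay in the sequence in which the CRF lists them. This is to be considered when the rules are applied.

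**Denominators.** The notes to SAP Tables 14.3.1.1 to 14.3.1.5 base percentages on all Safety subjects in the absorbency arm. The same notes define N per period (14.3.1.1) or per article (14.3.1.2 to 14.3.1.5). SAP 5 admits a woman to the Safety Population after one tampon of either product.

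**The concern.** In a two-period crossover, the date that separates the products is the second product's first insertion. A rule that fills dates from the 1st of the month or from the start of the study tends to put a partly dated second-cycle AE before that boundary. A single anchor suits the prior/concomitant medication split in SAP 9.6, but not a comparison of two products.

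AE frequency and severity by product are one of the two tolerability inputs in SAP 8.4. With randomized order, moving AEs from the second product to the first draws the two products' rates together and can soften a real difference. The denominator conflict is separate: a programmer cannot satisfy both the percentage note and N once some women have used only one product.

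**Working it through.** The plan states no figure for this point, so there is none to reproduce. I applied the SAP 6.1.5 rules and then the SAP 9.1 assignment.

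**Inputs**
- Gap between the two first insertions: 21 to 35 days, equally weighted (Protocol inclusion criterion 4; the gap is assumed equal to cycle length).
- First insertion: each of 365 calendar dates.
- True onset: each of W days starting with the second product's first insertion, equally weighted. W is not stated. AE collection is described as "Information about AEs will be collected from the Test Article Dispensation until the end of the study", and "Subjects will be considered to have completed the study after they complete the second post-use visit"; that visit falls within 72 hours of last use. An assumed 4 to 7 days of use plus 3 days gives W of about 7 to 10. W = 14 and 28 are wider checks; SAE collection runs 7 days longer.

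**One example.** First insertion 10 March, second product from 7 April, true onset 10 April. Day missing gives 1 April; month missing gives 10 March; both missing gives 10 March. All three precede 7 April, so all count under the first product.

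**Day missing.** The AE is misassigned unless a 1st of the month lies between the second product's first insertion and onset, inclusive. The share misassigned is 1 − (12/365) × (W + 1)/2, which the enumeration confirms:

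| W (days) | Enumerated | Share under first product |
|---|---|---|
| 7 | 33,285/38,325 | 86.8% |
| 10 | 44,850/54,750 | 81.9% |
| 14 | 57,750/76,650 | 75.3% |
| 28 | 80,226/153,300 | 52.3% |

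Reverse check: of 153,300 first-product onsets with the day missing, none moves to the second product.

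**Month and day missing.** The share is 100% when onset is in the same calendar year as first insertion. If the recorded year is kept and onset falls in the next year, the rule gives a date late in that next year, and the AE counts under the second product. With W = 7, onset is on average 28 + 3 = 31 days after first insertion, so the share over all start dates is 1 − 31/365 = 91.5%.

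**Only the month missing (W = 7).** At 21-, 28- and 35-day gaps the shares are 0%, 65% and 100% with no year end crossed, or 0%, 60% and 90% over all start dates keeping the recorded year.

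**Reverse movement across a year end.** For these last two cases, 5,810 of 153,300 first-product onsets (3.8%) move to the second product if the recorded year is kept.

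**Effect on a comparison.** Assume true AE rates of 10% (test) and 5% (reference), each product second for half the women, a share q of AEs lacking the day, and a misassigned share a.
- Test reads 10% − 5%·q·a + 2.5%·q·a = 10% − 2.5%·q·a.
- Reference reads 5% − 2.5%·q·a + 5%·q·a = 5% + 2.5%·q·a.
- Net shift per product in an arm of 369 (SAP 3.2) is 369 × 2.5% × q × a.

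| q | Ratio, a = 0.868 | Ratio, a = 0.523 | Net women per arm, a = 0.868 |
|---|---|---|---|
| 2% | 1.97 | 1.98 | 0.16 |
| 5% | 1.94 | 1.96 | 0.40 |
| 10% | 1.88 | 1.92 | 0.80 |

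The true ratio is 2.00.

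**Denominator.** If a share p of Safety women stop after cycle 1, evenly by order, each product was used by 1 − p/2 of them. A true 5.0% then reads 5.0% × (1 − p/2) = 4.9%, 4.8% or 4.5% for assumed p = 5%, 10% or 20%.

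**The case against.** **The precaution already covers this.** SAP 3.4 speaks of each tampon, test or reference, being administered for one cycle, so administration in the precaution could be read per product. That reading is available but not stated. The precaution is only to be considered and does not name the second product. Keeping the CRF order helps a second-product AE listed after another AE dated in that period; it does not help a woman with a single AE. At best the text is ambiguous.

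**Partial dates will be rare.** The Protocol (Recording Adverse Events) requires onset date and time, staff collect AEs at each post-use visit, and the study lasts about two months per woman. This stands: the documents give no rate of partial dates, 2% to 10% is assumed, and even 10% shifts less than one woman net per arm.

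**Randomized order balances the error.** It prevents the error from favoring one product systematically. It does not remove the dilution.

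**The denominator follows the general rule in SAP 4.1, and N is only a header count.** True as far as it goes, but the printed percentage would not equal n/N once anyone has used one product only.

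**Stronger readings to avoid.** A reader might infer that every partly dated second-product AE goes to the first product, or that movement is always one way. The rules do not support that: with only the month missing the share is 0% at a 21-day gap (7-day window), and across a year end some AEs move the other way. Nor is every date set from the first insertion; a day-missing AE in a later month goes to the 1st of that month.

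**Conclusion.** The point holds and is minor. As written, SAP 6.1.5 fills partial AE dates without the date on which SAP 9.1 depends. For second-product AEs lacking the day, a majority is counted under the first product in every window tried, and more than 80% in the 7- and 10-day windows that best match AE collection. Month-only gaps depend on cycle length, and the two month-missing cases also depend on how a year end is handled.

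These shares rest on evenly spread onset, a gap equal to cycle length, and an assumed window. The effect on the product comparison rests further on assumed AE rates and an assumed share of partial dates; it is a slight dilution, not a bias toward the test tampon.

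A reader might infer that the tolerability conclusion is at risk. The documents do not support that: acceptable tolerability has no numeric limit (SAP 2.1.1), so no pass/fail result flips. The denominator conflict lowers both products' rates slightly and about equally, and only if some women use one product.

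**What to change.** 1. **Partial AE dates (SAP 6.1.5).** Use the cycle-level first insertion dates already derived there. Where the known date parts identify the period, or the recording visit or cycle does so if the CRF holds it, impute within that period. For example, the second box is dispensed at Visit 2 (women outside the exam subset) or Visit 3 (subset), so an AE recorded at Visit 2 cannot belong to the second product. Otherwise list the AE as ambiguous and show the AE tables under both assignments.
2. **Denominators (notes to Tables 14.3.1.1 to 14.3.1.5).** Divide each product column by the Safety women who inserted at least one tampon of that product, and make the percentage note agree with N.

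The cost is SAP wording and footnote edits, a short list of ambiguous AEs, and product-specific denominators to derive. The insertion dates are already derived. The recording visit is not shown to be available: AE Listing 16.2.7.1 has no such field, so check the CRF before relying on it.

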7.1. Disposition of Subjects and Withdrawals

The number of subjects randomized, the number of subjects completing, the number of subjects who withdraw early (including tabulated reasons for discontinuation from the study), and the number of subjects in each analysis population will be tabulated by absorbency arm and overall.

7.2. Protocol Violations and Deviations

Protocol deviations will be classified as minor or major and will be presented in a data listing.

7.3. Demographics and Other Baseline Characteristics

Demographic variables such as age, sex, race, and ethnicity will be summarized overall and by absorbency arm. Baseline characteristics such as the number of tampons typically used during period and the tampon absorbency used most often will also be summarized.

Demographic and baseline characteristic data will be summarized by absorbency arm and overall for the ITT population.

7.4. Exposure and Compliance

The number of used and unused tampons returned and the frequency and percentage of diaries returned with an entry present for each used tampon will be summarized by absorbency arm and overall for the Safety population.

Test article and diary dispensation information and diary review information will be listed.

8. Validation Criteria Analysis

All the analyses performed to assess whether validation criteria have been met will be performed separately for each absorbency arm, with the exception of the analysis of the packaging and labeling interview responses which will be analyzed for both absorbencies combined.

8.1. Elongation

Descriptive statistics will be reported for the length of elongation of used tampons within each test article type (test or reference tampon), and separately for each absorbency arm, in the MITT population. The number and percentage of used tampons that have elongated will be reported for test tampons and reference tampons. Determination of whether a tampon is considered to have elongated is described in Section 6.1.4. The denominator for the percentage calculation will be based upon the number of used tampons returned within each test article type (test or reference tampon) and within each absorbency arm (regular or super). The 95% CIs for the percentage elongated estimates will be computed using the exact method (Clopper & Pearson, 1934).

In addition, the testing of equality of proportions of elongation between test and reference article types within each absorbency arm will be performed. For this purpose, the difference between proportions will be calculated along with 95% Wald CIs. Pearson chi-square test will be computed in support of hypothesis testing. The samples for comparison will be considered independent.

The following hypothesis will be tested:

H0: $p1-p2=0$. There is no significant difference in the tampon's elongation rate between the test and reference article types within each absorbency arm.

H1: $p1-p2\neq0$. There is a significant difference in the tampon's elongation rate between the test and reference article types within each absorbency arm.

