### **Test Article Dispensation, Collection, and Management**

The following items will be dispensed to the subject at the visit prior to product use:

- 1 box of tampons according to the randomization schedule
- 1 used tampon collection kit containing the following:
  - 16 small clear sealable individual used tampon collection bags
  - 1 medium sized red sealable bag to collect all individually sealed tampon bags
- 1 diary containing study instructions and diary entry forms for each tampon used
- 1 cooler bag (dispense 1 per subject for the entire study)
- 1 freezer pack
- 1 large opaque white drawstring bag used to return the cooler bag containing the red tampon collection bag, completed diary, and any unused tampons to the site

Subjects will collect each used tampon and place it in a clear bag, labeled with the following information:

- Study Number
- Subject Number
- Menstrual Cycle (1 or 2)
- Tampon Number (e.g., #1, #2, #3, etc.)
- Tampon Code (CR, CS, BR, or BS)

Each of the clear bags containing a used tampon will be placed inside of the single red sealable bag and placed in the freezer until returned to the clinic. The red bag will be labeled with the following information:

- Study Number
- Subject Number
- Menstrual Cycle (1 or 2)

- Tampon Code (CR, CS, BR, or BS)

If a subject is not at home at the time of tampon removal, the subject can place the tampon in the clear collection bag in the cooler bag provided until the subject returns home and can place it in the red bag in the freezer.

Following the last tampon use, subjects will return to the clinic, with the following items in the white drawstring bag provided:

- cooler bag containing the red tampon collection bag with all used tampons
- completed diary
- all unused tampons.

Study staff will document the number of used and unused tampons collected, verify that there is a diary entry for each used tampon, verify the accuracy and completeness of diary entries, and address and document any discrepancies.

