3.2. Sample Size and Power

The sample size was calculated for a single absorbency and is based on the assumption that 0.7% of reference tampons elongate (>10 mm) upon removal and 0.2% of test tampons elongate upon removal. An estimated yield of 43.75% was used, where yield is the number of usable tampons for the elongation analysis divided by the total number of products given to the subjects (i.e., yield means the percentage of tampons given to each subject that were used and can be included in the elongation analysis). It is assumed that subjects are given 16 reference tampons and 16 test tampons and use 7 tampons in each cycle.

With a power of 80% and a 2-sided alpha of 0.05, assuming 2 tampon types tested (reference and test) and each subject receiving 16 products per cycle, a total of 369 subjects will need to be enrolled in the study for each absorbency. Since there are 2 absorbencies, the study will enroll 738 subjects.

For each absorbency this translates into needing a total of 5,166 used tampons (2,538 used tampons for each tampon type (reference and test)).

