6.1. Statistical Definitions and Algorithms

6.1.1. Handling of Dropouts or Missing Data

In general, missing data will not be imputed unless otherwise stated.

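### The elongation rate divides by all used tampons returned, so a returned tampon without a measurement in effect counts as not elongated

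*SAP*

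**What the plan says.** SAP 8.1 sets the denominator: "The denominator for the percentage calculation will be based upon the number of used tampons returned within each test article type", within each absorbency arm. The note to the Table 14.2.1 shell repeats this for the MITT population, so it is not a slip in one place. SAP 6.1.4 sets the numerator: a tampon is elongated only if it has a measurement above 10 mm. Under Tampon Assessment Procedures (protocol section 8), staff measure every used tampon and enter 0 mm when nothing protrudes. A true non-event therefore has a recorded value, and a blank means something else.

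The plan expects some tampons to be unassessable. MITT membership (SAP 5) needs at least one returned tampon that can be assessed, and Listing 16.2.6.1 has a field for why an assessment was not done. Neither removes a single unmeasured tampon from the denominator. On missing data, SAP 6.1.1 says: "In general, missing data will not be imputed unless otherwise stated".

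The sample size rests on another base. SAP 3.2 says "An estimated yield of 43.75% was used" and that "yield is the number of usable tampons for the elongation analysis divided by the total number of products given to the subjects".

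The validation criterion (SAP 2.1.1; protocol section 11) asks only that the test rate be no higher than the reference rate in each absorbency, with no margin. SAP 4.1 calls the assessment of the criteria descriptive. SAP 8.1 adds a chi-square test in support.

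On accountability, protocol section 9 has site staff count used and unused tampons, "verify that there is a diary entry for each used tampon", and resolve discrepancies.

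**The concern.** Numerator and denominator are drawn from different sets of tampons. An unmeasured tampon cannot be an event but still counts as a trial, so the analysis treats unknown as not elongated. The protocol's 0 mm entry keeps the two apart in the data, and the SAP's percentage merges them again.

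This is the primary endpoint, and it is judged on point estimates with no margin. A product whose tampons are harder to assess, or whose assessments are missed more often, gets a lower reported rate for that reason alone. There is also a presentational problem. SAP 4.1 bases continuous summaries on non-missing values, so within Table 14.2.1 the mean length and the percentage elongated can rest on different numbers of tampons. The shell does not print the denominator of the percentage.

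**Working it through.** **1. The plan's own figure.** Inputs from SAP 3.2: "With a power of 80% and a 2-sided alpha of 0.05"; "0.7% of reference tampons elongate (>10 mm) upon removal and 0.2% of test tampons elongate upon removal"; subjects "use 7 tampons in each cycle", and 7/16 = 43.75%. The arcsine formula is n = 2(z₀.₉₇₅ + z₀.₈₀)²/h², with h = 2·asin√0.007 − 2·asin√0.002. It gives 2,576.5, so 2,577 tampons per type. Then 2,577/7 = 368.1, rounded up to 369 subjects, and 369 × 7 = 2,583 per type, 5,166 in all. This matches the protocol. SAP 3.2 prints 2,538 per type, but its own total of 5,166 requires 2,583, so I use 2,583. These are usable tampons, not returned ones.

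**2. Expected events.** Reference: 0.007 × 2,583 = 18.1. Test: 0.002 × 2,583 = 5.2. The gap is about 13 tampons.

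**3. Effect of the denominator.** With R returned, a share u unmeasured and true rate p among those measured, the reported rate is p·R·(1 − u)/R = p(1 − u). For test and reference, the ratio of reported rates is the true ratio × (1 − u_T)/(1 − u_R). If u_T = u_R the order is unchanged.

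**4. Effect on the criterion.** P(pass) = Σₓ P(X_T = x)·P(X_R ≥ x), with independent binomials, 2,583 returned per product and the rates from step 3. All shares are assumed.

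| True test / ref | Unassessable test / ref | Reported test / ref | P(pass) |
|---|---|---|---|
| 0.7% / 0.7% | 0 / 0 | 0.700% / 0.700% | 0.53 |
| 0.7% / 0.7% | 5% / 0 | 0.665% / 0.700% | 0.59 |
| 0.7% / 0.7% | 10% / 0 | 0.630% / 0.700% | 0.65 |
| 0.7% / 0.7% | 10% / 2% | 0.630% / 0.686% | 0.63 |
| 0.7% / 0.7% | 20% / 0 | 0.560% / 0.700% | 0.77 |
| 0.8% / 0.7% | 0 / 0 | 0.800% / 0.700% | 0.37 |
| 0.8% / 0.7% | 12.5% / 0 | 0.700% / 0.700% | 0.53 |

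In the last row a test product that is truly worse looks identical to the reference. At the planning rates, by contrast, the order would reverse only if more than 1 − 0.2/0.7 = 71% of reference tampons were unassessable with no test tampon unassessable. The rule matters when the true rates are close, not when they are as far apart as planned.

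**5. Tipping point for tampons not seen.** Start from 18 and 5 of 2,583. Add only elongated test tampons, to numerator and denominator, and no reference events. With 13 more, test is 18/2,596 = 0.693% against 18/2,583 = 0.697%, which passes. With 14 more it is 19/2,597 = 0.732%, which fails.

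Now count all unreturned test tampons and assume reference losses are unrelated to elongation. The elongation rate needed among the unreturned test tampons for test to reach 0.7% is:
- 1% of used tampons unreturned (26): 50%
- 5% (136): 10%
- 10% (287): 5%
- 20% (646): 2.7%

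**6. Supportive test only.** The Pearson p-value, uncorrected, is 0.0066 at 18 vs 5. With 4 more elongated test tampons it is 0.082.

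**The case against.** The SAP never says that an unmeasured tampon counts as not elongated. The usable-tampon yield and the MITT wording suggest that measured tampons may have been intended. If few tampons are unassessable, or the share is equal across products, the criterion is unaffected, and no passage suggests that the shares differ. All of this stands as a limit on size. It does not remove the point, because SAP 8.1 and Table 14.2.1 both state the denominator and a programmer following them would get the diluted rate.

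A reader might go further and infer that unreturned tampons go unchecked and that a handful could overturn the result. The documents do not support that:
- The p-value shift in step 6 cannot change the validation outcome, which is a comparison of point estimates.
- Equal rates pass, so at the planning rates reversal needs 14 hidden elongated test tampons and no hidden reference ones. At 5% unreturned, the required 10% elongation rate is about 50 times the planned 0.2%.
- If elongated tampons are less often returned whatever the product, more reference events are lost at the planning rates and the gap narrows. That works against the test product. Harm needs selective loss of elongated test tampons, which nothing in the documents indicates.
- The counts are largely planned by product: diary entries (Table 14.2.2.1), returned tampons (Table 14.1.3) and tampons with a length (Table 14.2.1), with tampon-level listings. They are not set side by side, and the first two use the Safety population while the third uses MITT.

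**Conclusion.** The concern holds for the denominator. As written, SAP 8.1 understates each product's elongation rate by the factor (1 − unassessable share) and favours the product with the larger share. It also uses a different base from the sample size.

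The size depends on a share that the documents do not give. An equal share leaves the order of the rates unchanged. With true rates equal at 0.7%, 5% to 20% unassessable test tampons against none for reference raise the chance of passing from 0.53 to between 0.59 and 0.77. These probabilities assume independent tampons and 2,583 returned per product. At the planning rates the rule would not plausibly change the outcome.

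That the SAP deliberately scores unassessable tampons as non-events is a stronger reading than the text allows; the effect follows from the stated denominator. For unreturned tampons, what remains is a gap in presentation and sensitivity analysis, not a demonstrated bias.

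**What to change.** In SAP 8.1 and the Table 14.2.1 note, define the denominator as returned used tampons with a recorded elongation measurement, including 0 mm, by product and absorbency. Print that count in the table. The exact intervals, the difference in proportions and the chi-square test should use the same base.

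As a supplement, add one display in a single population, by product and absorbency, with tampons used (diary), returned and measured side by side. Add a tipping-point line: how many unreturned or unmeasured test tampons would have to be elongated, with no such reference events, for the test rate to exceed the reference rate.

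The cost is a change of SAP wording, one revised shell and one short table. All the data are already collected, and nothing changes for sites or subjects.
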